## Page 9:

• Under section **TEST SITES**, 1st paragraph, line 1 – Please delete the word "in" after the words "will be performed".

## Page 10:

• Under 8th paragraph, line 2 – Please replace the words "we are able make" with the words "we are able **to** make".

## Page 11:

• 1st paragraph, top of page, line 3 – Please replace the words "test subject" with the words "test subjects". (add an "s" to the word "subject").

## Page 16:

• Under section **TEST SUBJECTS**, Eligibility Requirements, Literacy – Please replace the words "and understand English" with the words "and understand English sufficiently enough to follow directions".

## Page 17:

- Under 1st paragraph, item #6, line 1 Please replace the words "by previous" with the words "by previously".
- Under 1st paragraph, item #7, line 1 Please replace the words "beverages 12 hours" with the words "beverages for 12 hours".

April 3, 2007 Page 2 of 4 G0590307001A044

#### Page 18:

• Under section 5th paragraph, line 8 – Please replace the words "presence of a witness" with the words "presence of the person obtaining consent."

## Page 26:

• Sheet title **APPENDIX II: DATA COLLECTION SHEET** - This page states "Appendix II, Data Collection Sheets" but the Table of Contents states "Appendix I" for page 26. Is there an Appendix I? Please clarify.

NOTE: When making the revisions to the Protocol, please remember to update the version date before re-submitting.

The Consent Form (dated 3/26/07) was conditionally approved pending the following modifications recommended by the board:

## Header:

All pages - Please provide a "Version Date" in the header for all pages.

#### Page 1

- Under section **Address** Please provide the address of the study sites where the study will take place.
- Under section **Purpose of Study**, line 3 Please replace the word "mosquitoes." With the words "mosquitoes in Georgia and Florida."
- Under section **Purpose of Study**, line 12 Please re-write this sentence as follows: "If you decide to participate, sign the ICD in our office, after which you will receive a signed copy."
- Under section Suitability Checklist for the Study, item #3, lines 2 & 3 Please add "hyphens' between the words "over the counter". Also, please replace the words "pregnancy test" with the words "urine pregnancy test".
- Under section Suitability Checklist for the Study, item #5 Please reformat to move this item to the next page so the word "below" is not a stand-alone word on page 2.

#### Page 2:

- Under item #7 Please replace the words "You must be comfortable "with the words "You must not be bothered".
- Under item # 12 Please tell which "study site" the subject will go to.
- 1st paragraph after the numbered items, line 1 Please add a description of who the "control subjects" are.
- Under section **Procedures**, **Prior to the test**, item #1, lines 3 to 6 Please delete the sentence beginning with the words "If you do not want to visit". The consent form should be signed in the presence of study personnel.

## Page 2 (continued):

• Under section **Procedures**, **On the morning prior to the study day**, item #1, lines – After the word "to share lodging." please add the sentence "You will bring the following clothing with you: "and describe the articles of clothing.

#### Page 3:

- Under section **Study Details**, item #2, line 2 Please replace the words "you are a control and" with the words "you are a control **subject** and".
- Under section **Study Details**, item #8, line 8 Please replace the words "parts of their arms" with the words "parts of his/her arms".

## Page 4:

• 1st paragraph after the numbered items, line 1 – Please replace the words "your limbs" with the words "your arms".

#### Page 5:

- 1st paragraph, top of page, line 2 Please clarify who it is that will "lean over to bite your treated skin".
- Under item #2, 2nd paragraph, line 6 After the words "permethrin spray." please add the following sentences: "Tuck the pants into your socks. Clothing will be inspected to ensure the least likelihood of a tick getting on your skin."

#### Page 6:

- Under section **Financial Consideration**, line 8 Please delete the extra "period" after the word "possible".
- After the section Alternative Please add a "Blank Box" with the words "This space intentionally left blank" in the center of the box." There can only be 1" or less of space between the footer and the last line of the last paragraph of the page.

Page 17; Under the 1st paragraph, item #7, line 1, the words "beverages 12 hours" will be replaced with "beverages for 12

hours".

Amendment #9:

Page 18; Under the 5th paragraph, line 8, the words "presence of a witness" will be replaced with "presence of the person obtaining

consent."

Amendment #10:

Page 26; The words "Appendix II" will be changed to "Appendix

Impact On The Study:

Amendments #2 and #9 require that the informed consent be

signed by the test subjects in the presence of the Principal

Investigator or his representative. The other amendments change

wording to clarify the intent of the protocol.

Submitted by:

Approved by QA:

Acknowledged by: Sponsor Representative

#### Good Morning:

The Protocol Amendments #1 to 8 (dated 4/5/07) were approved on April 6, 2007.

The Consent Templates (dated 4/5/07) were approved on April 6, 2007.

We also reviewed the Site Submission for both the Savannah, Georgia and Pine Island, Florida sites and found the following items that need to be addressed:

# Site Application Letter (both sites)

- Page 1, Question 2a Please list the 24 hour emergency phone number on this form. Also, please clarify the 24 hour phone number on page 1 of the Consent Form - does it go to an answering service? Voice mail? Cell phone?
- Page 3, Question 13a The question asks "how do you recruit subjects". The answer was "via telephone". Please clarify from where do you recruit the subjects that you phone? - Advertisements? Data base of previous subjects?
- Page 4, Quesiton 16b Please provide an answer to this question. If there are no other individuals involved in the study, then write "none".

## **ADVERSE EVENTS**

Unexpected adverse reactions from a study subject must be reported in writing to the EIRB and sponsor by the investigator or his/her designee within ten working days. If the reaction is serious (fatal, life-threatening, permanently disabling or requires hospitalization) and may be reasonably caused by the test article, it must be reported immediately in writing to the EIRB and the sponsor. Additional written follow-up reports may be necessary until the adverse event is resolved.

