#### STUDY RATIONALE

This study will evaluate the efficacy of two picaridin-based repellents which have not been previously tested in the field for a duration of up to 12 hours. Presently there are 15 picaridin-based insect repellent products registered under FIFRA. The products range from 5% picaridin to 20% picaridin and include pump spray, aerosol, lotion, and towelete applicator products. ICR has previously evaluated Picaridin-based repellents in both the laboratory and in the field for efficacy. We have found these types of repellents to be efficacious in the laboratory as well as in field studies for up to and beyond 8 hours. In previous studies we have seen no indication of any type of reaction from these repellents, or cause for concern regarding safety issues.

Field studies, such as the one proposed, have been long considered by regulatory authorities and the scientific community to be the most realistic and reliable method for testing the performance of a topically applied insect repellent product. Under FIFRA, EPA requires submission of such human efficacy study data (EPA/OPPTS Guideline 810.3700) in support of insect repellent product registration. Each new insect repellent formulation must have performance studies conducted on human subjects to substantiate the product's label claims.

Each product is unique and will provide different protection times for different pests depending on both its percent active ingredient and formula composition

The prominent risks associated with the proposed field study to assess the performance of these insect repellent formulations are the potential for allergic or irritation responses to the test materials and mosquito bites, and the potential risk of contracting a mosquito or other insect-borne disease. Both of these risks, skin reactions and the disease threat, were significant factors that were considered in detail and addressed in the development of the proposed study design.

Page 3 of 31

Mosquito Repellent Field Test, Florida & Georgia

Protocol No.: G0590307001A044 ICR Project No.: 0307-059-0155

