#### TEST SITES

This study will be performed in two different times at two different sites. Two sites will be chosen based upon the absence of mosquito-borne disease and adequate mosquito populations. The first site will be at the following address:

The Savannah-Ogeechee Canal Museum & Nature Center [name] Savannah, Georgia 31419

The second site will be at the following address:

Pine Island, Florida Lee County Mosquito Abatement District

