#### **NEGATIVE CONTROL**

Sufficient biting pressure (i.e., mosquito landing rates in the range of 1 to 10 per minute in a 250 cm^2 area on each of the exposed untreated control arms for up to a 5 minute period) will be confirmed at the commencement of the study and throughout the study. One untreated arm of each of the two control subjects will serve as negative controls. These controls will be selected at random from the total pool of test subjects by drawing names. Different subjects will be used as controls for each day of the study. This will be accomplished by removing the names of subjects already used as negative controls from the pool when drawing names of subjects to be used for the next day's test.

Negative controls will be used to monitor the level of mosquito activity in the area by baring the 250cm² untreated area on their arm for up to five minutes every one-half hour while the study director or an assistant counts the number of mosquitoes which land on the bare skin. If the stated landing rate has been verified prior to the end of the five minute period, the control will stop exposing their bare arm to mosquitoes. To minimize the number of bites, the mosquitoes will be brushed away with the tip of a pencil or pen after being counted. The negative controls are also protected by covering the untreated test area with the shirt sleeve in between the 5-minute test sessions. Like the treated test subjects, the negative controls will be protected with a head net and latex or vinyl gloves.

The negative controls will not be exposed to any repellent related risk.

Page 11 of 31

Protocol No.: G0590307001A044 ICR Project No.: 0307-059-0155

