#### RISK CHARACTERIZATION AND MINIMIZATION

The subjects will be exposed to three types of risk:

1. They will be treated with a test repellent.

The active ingredient, Picaridin® demonstrates a low acute oral, dermal and inhalation toxicity. It is classed as Category IV for acute inhalation toxicity and primary dermal irritation. It is not a dermal sensitizer. The EPA "New Pesticide Fact Sheet" indicates that the toxicology data base for the active ingredient is complete and no additional studies are required.

There is minimal risk for subjects to experience an adverse reaction to the insect repellents being tested. The study sponsor that developed the test repellents has over 120 years of experience formulating and producing a wide variety of cosmetics and personal care products with worldwide sales.

All of the inert ingredients used in the finished insect repellent products have a long history of safe use in various personal care and cosmetics products.

Moreover, the sponsor has confirmed that all of the inert ingredients used in each of the test repellents have been previously reviewed and approved by EPA for use in FIFRA registered insect repellent products.

While there is low concern for the toxicity potential for the test samples to induce an adverse reaction in the test subjects, they will be monitored throughout the study and prompt medical attention will be obtained if any adverse reaction is observed among the subjects on test. Those individuals who are known or claim to have allergies to mosquito bites, insect repellents, or skin care products will be excluded from participation in the study.

2. They will be exposed to bites from mosquitoes.

All subjects known to have severe reactions to mosquito bites will be excluded from this study.

All subjects will be issued head nets and a choice of latex or vinyl gloves. Only a small area (250 cm²) of skin on each arm will be exposed. All other parts of the body will be covered with the subject's personal clothing. The exposed areas will be covered immediately upon receiving a FCB on that area. Caladryl® or Calamine® lotion and rubbing alcohol will be available at the study site for use to mitigate any reaction to mosquito bites.

3. They may be exposed to vectors of arthropod-borne diseases

Page 13 of 31

Mosquito Repellent Field Test, Florida & Georgia

Protocol No.: G0590307001A044 ICR Project No.: 0307-059-0155

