#### REQUIRED REPORTS

Approval for a site is granted, in most cases, for one year from the date of the approval. The expiration date for your approval is included in your approval letter and stamped on the first page of your approved consent form. Any data generated using research subjects after that date will be invalid. If you plan to continue the project, an Extension Report must be filed within the 30 days prior to your site expiration date.

if your research has ended, a Final Report must be filed within 90 days of the study completion date. A Request to Increase Number of Patients Report must be filed prior to increasing enrollment of participants at any point in the study.

These reports must include the following information: number of subjects enrolled (signed the consent form), number of subjects discontinued (and the reasons why), number of subjects still participating, the completion date of the research (Final Report only) and an outline of any adverse events encountered. The report must be signed by the Principal Investigator or his/her designee. To simplify the reporting process, you may obtain a standardized form from the EIRB that can be utilized for any of the above reports.

REVISIONS

Revisions to the protocol or consent form must be reviewed and approved by the EIRB prior to implementation.

Protocol Revisions - changes to the protocol can be submitted either as an amendment or revised protocol. For ease of review, an outline of the specific areas of the protocol that were changed should accompany the amendment or revised protocol.

Consent Form Revisions - when submitting revisions to a previously approved consent form, an investigator or designee needs to submit three copies of the revised consent form for approval along with an outline of the specific changes made. If changes are made to the approved template text, the revision date of the consent form must be updated.

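### Immediate reporting of a serious event depends on possible causation by the test article, so serious harm from mosquito exposure, and any serious event in an untreated control, is not immediately reportable

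*Protocol*

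**What the plan says.** The Adverse Events section has two tiers. The general tier reads "Unexpected adverse reactions from a study subject must be reported in writing to the EIRB and sponsor by the investigator", and its deadline is ten working days. It sets no condition on cause and does not leave out controls. The immediate tier applies when a reaction is serious (death, threat to life, permanent disability or hospital admission) "and may be reasonably caused by the test article, it must be reported immediately in writing to the EIRB and the sponsor". Both conditions must be met.

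The Required Reports section adds that the periodic reports must outline any adverse events, and that "a Final Report must be filed within 90 days of the study completion date".

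The protocol body lists three risks under Risk Characterization and Minimization. The first is treatment with the repellent. The second is "They will be exposed to bites from mosquitoes". The third is exposure to vectors of arthropod-borne disease. Study Rationale likewise names skin reactions "and the potential risk of contracting a mosquito or other insect-borne disease". On the controls, the Negative Control section says: "The negative controls will not be exposed to any repellent related risk".

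On timing, Test Sites says: "This study will be performed in two different times at two different sites".

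**The concern.** In most product trials the product is the main source of study-related harm, and tying urgent reporting to the product is natural. Here the study procedure is itself a hazard: subjects bare skin to wild mosquitoes every half hour for up to 12 hours. The protocol calls the risk of an adverse reaction to the repellent minimal. It says the disease risk is low but cannot be fully removed, and it records a 2006 West Nile case in the county of the Georgia site. The urgent tier is keyed to the first of these hazards and does not reach the other two.

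What is at stake is subject protection, not the protection-time estimate. If a subject at the first location is hospitalised because of bites, the board and the sponsor may have no report before a second group is exposed in the same way at the other location.

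**Working it through.** No sample size, power or error rate is involved. The check applies each reporting condition to each kind of serious event that the protocol foresees.

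**Inputs**
- Reporting conditions: Adverse Events and Required Reports.
- Named risks: Risk Characterization and Minimization (three items).
- Groups per location: 12 treated and 2 untreated controls, 14 in all (Subjects; Treatment Groups).
- Exposure of controls: untreated skin, no product (Negative Control; Treatment Application).

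**Conditions applied to serious events**

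| Serious event | Immediate tier (needs possible causation by the test article) | Ten-working-day tier (needs unexpected) | Outline in periodic or final report |
|---|---|---|---|
| Product reaction, treated subject | Yes | Yes, if unexpected | Yes |
| Bite reaction, treated subject | Not if the bites alone are the cause | Only if judged unexpected | Yes |
| Bite-borne infection, treated subject | No | Only if judged unexpected | Yes |
| Any event, untreated control | No: no product was applied | Only if judged unexpected | Yes |

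Of the three named risks, 3 − 1 = 2 lie outside the immediate tier on its plain wording. In each location's group, 2 of 14 subjects have no product on the skin while they serve as controls, so no event arising from that role can meet the causal condition.

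**Is the immediate tier narrower still?** Its sentence refers back to the reaction in the sentence before, which concerns unexpected reactions. Read strictly, immediate reporting may itself require unexpectedness. The conclusion does not depend on this reading.

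**Does the ten-working-day tier close the gap?** It has no causal condition and covers any subject. A hospitalised bite reaction would probably be judged unexpected and so be reported. The point can be disputed, because bites and infection are named risks in Study Rationale, Risk Characterization and Minimization, and Discomfort and Hazard. Where the tier applies, ten working days is 10 ÷ 5 = 2 weeks, about 14 calendar days without holidays. The site application describes this laboratory's studies as lasting parts of one or two weeks, so a report could be on time and still arrive after fieldwork has ended. The protocol does not state the interval between the two locations.

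**Does the visible protocol body fill the gap?** Its table of contents lists no adverse-event or reporting section. Risk Characterization and Minimization provides monitoring and medical attention. Discomfort and Hazard tells subjects to seek care and send bills to the laboratory. Criteria for Test Cancellation makes health concerns a possible reason to cancel. None of these requires a report to the board or sponsor.

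**The case against.** **The source is probably not the sponsor's text.** The submission's index places the protocol on pages 10-41 and a board brochure on pages 160-161, and the reporting text reads as general guidance. This stands: the sponsor does not appear to have chosen the wording. It still governs the investigator, and it leaves the protocol free to be stricter.

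**A reader might infer that this is the only safety-reporting rule of the study.** The documents do not support that. Parts of the submission, including the consent documents, were removed before review, and the laboratory's and board's operating procedures are not shown. The general tier and the adverse-event outline are also reporting rules. The point is limited to prompt reporting in the text shown.

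**A reader might infer that serious bite-related events go unreported, or wait until 90 days after completion.** That is too strong. Subjects with known severe bite reactions are excluded, and testing proceeds only if disease surveys are negative. A hospitalised event would therefore most naturally count as unexpected and be due within ten working days. The longer delay arises only if the event is classed as expected.

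**A reader might put the affected group at 4 of 28 subjects.** That assumes one test day per location and fixed roles. The Negative Control section draws different controls for each day of the study, so the count is not fixed.

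**A treated subject's bite reaction may qualify.** Product covers the skin being bitten, and possible causation is a low bar. This stands for ambiguous skin reactions. It does not help for bite-borne infection or for controls.

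**The same team runs both locations.** The investigator would know of a test-day hospitalisation and may cancel, and the Schedule of Events includes a verbal report at the end of the test, with no recipient named. This weakens the consequence but does not remove it: cancellation is discretionary and neither step requires notice to the board. An illness that appears after the test day reaches the laboratory only if the subject tells it.

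**Conclusion.** The point holds in a limited form. In the text shown, immediate reporting is conditional on possible causation by the test article. Serious events caused by bites or bite-borne disease (two of the three named risks), and any serious event in an untreated control, do not meet that condition. They fall to the ten-working-day tier if judged unexpected, and otherwise only to the adverse-event outline.

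This rests on three assumptions: the Adverse Events text applies to this study as written, no removed passage or unseen procedure sets a stricter rule, and causation by the test article does not include causation by the exposure procedure. The consequence for the second location also depends on the interval between locations, which is not stated. The reporting rule does not match the hazards the study creates. It is a cheap improvement to subject protection and has no bearing on the efficacy analysis.

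**What to change.** Add one sentence to the protocol's Risk Characterization and Minimization section: any serious event, as the Adverse Events section defines serious, in any treated or control subject, that may reasonably be related to the test article or to a study procedure, including exposure to mosquitoes, is reported immediately in writing to the EIRB and the sponsor, whether or not it was expected.

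The board's guidance can stay as it is. The change concerns reporting only and proposes no treatment, stopping or cancellation rule. The cost is one amendment, which needs board approval before use, and probably a few more expedited reports. It needs no extra subjects, staff or procedures.
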